## **9.0 Direct Access to Source Data/Documents**

Only study investigators ([name], [name], and [name]) will have direct access to study related documents.

## **10.0 Quality Control and Quality Assurance Procedures**

Study investigators will review data collection forms as well as the completeness of the questionnaires when data is collected to ensure accuracy and completeness.

## **11.0 Ethics**

### 11.1 Consent process

All patients will provide written informed consent prior to study participation. Patients identified with PAD will be referred by their vascular surgeons to the TRI cardiac rehabilitation program. Upon the initial assessment at the Rumsey Centre, PAD patients will be informed about participating in the proposed study by a cardiac rehabilitation staff member. If the patient is interested, the cardiac rehabilitation supervisor will introduce the patient to one of the study investigators to provide the potential participant with further study details. If the patient wishes to participate in the study, they will provide written informed consent.

CAD patients who have attended an initial assessment and have consented to chart review will have their patient file reviewed to determine if the patient is an appropriate match to a PAD patient based on sex, age ( $\pm 5$  years), presence of diabetes, and assigned

## Comparing the efficacy of cardiac rehabilitation for patients with peripheral artery disease to patients with coronary artery disease/Protocol #03

cardiac rehabilitation supervisor. A cardiac rehabilitation staff member will inform the patient about the research study. If the patient expresses interest, they will be introduced to one of the study investigators who will provide further study details during their second assessment.

### 11.1.1 A description of the identification process

TRI is launching a Vascular Program designed to support patients with PAD seeking opportunities to manage their condition. All patients part of the Vascular Program will be referred by vascular surgeons. The cardiac rehabilitation staff helping with the Vascular Program will be informed about this proposed research study and will introduce all PAD patients to the opportunity. If patients express an interest in learning further details, the staff member will introduce the patient to one of the study investigators.

CAD patients will be identified through consented chart review. All patients in the cardiac rehabilitation program at TRI are asked during the initial assessment whether they would like to consent to a chart review by research personnel as part of standard procedures. The study investigators will review the patient charts to find a match to a participant with PAD. The study investigator will notify the cardiac rehabilitation staff members conducting the exercise stress test to inform the patient about the study. If the patient expresses interest in learning further details, the staff member will introduce the patient to one of the study investigators.

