## Comparing the efficacy of cardiac rehabilitation for patients with peripheral artery disease to patients with coronary artery disease/Protocol #03

Hospital to the TRI cardiac rehabilitation program. Upon the initial assessment at TRI, PAD patients will be informed about participating in the proposed study by the principal investigator. CAD patients who have attended an initial assessment and have consented to chart review will have their patient file reviewed to determine if the patient is an appropriate match to a PAD patient based on sex, age, presence of diabetes, and assigned cardiac rehabilitation supervisor. One of the study investigators will then inform the patient during their second assessment at TRI about the study and invite the patient to participate in the study.

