#### 3.2 Study hypothesis

The primary hypothesis is that patients with CAD will have greater improvements in  $VO_2\text{peak}$  and 6-minute walk test compared to patients with PAD (Lucini et al., 2002; Parmenter, et al., 2015). However, considering the walking limitations patients with PAD often have and the improvements observed with exercise training (Milani & Lavie, 2007; Novakovic et al., 2016), it is hypothesized that patients with PAD will have greater improvements in the WIQ and QOL compared with patients with CAD. Furthermore, a secondary hypothesis that the magnitude of response for patients with PAD will be dependent on biological sex and type of PAD. Lastly, it is hypothesized that patients with PAD on average will have a greater exercising heart rate, rating of perceived exertion and rating of pain severity compare to patients with CAD.

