### **8.2 The number of subjects planned to be enrolled**

Sample size calculations were conducted using an alpha of 5% and a power of 0.8. Calculations were based on the primary and secondary variables of interest ( $VO_2$ peak

Comparing the efficacy of cardiac rehabilitation for patients with peripheral artery disease to patients with coronary artery disease/Protocol #03

and 6MWT distance) for PAD and CAD patients. To be conservative, the largest sample size (6MWT) was selected.

Previous literature has found that patients with PAD undergoing exercise training compared to PAD patients who did not undergo exercise training had improvements in the 6MWT of 34.9m (95 % CI 25.6–44.1 m,  $P<0.00001$ ) (Parmenter et al., 2015). In contrast, patients with CAD had improvements of  $29.6\pm12$ m following exercise training (Jaureguizar et al., 2016). Clinically significant changes have been defined as 20m for the 6MWT (Perera et al., 2006). A difference of 10 meters between groups is a conservative average between what is observed in the literature and the defined clinically significant change. The sample size calculation for a power of 0.8 would be 23 participants per group. Accounting for a 20% drop out, 28 patients with CAD and 28 patients with PAD will be recruited. Statistical significance will be set at a  $P$  value of 0.05.

A sample size of 28 participants per group is powered to detect a difference of 1.6 ml/kg/min between groups for VO2peak.

8.3 Procedure for accounting for missing, unused, and spurious data.

If data variables are missing, the whole participant data set will be excluded from the main statistical analysis. If some data is available, the participant's data will be included in the intention to treat analysis.

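### When several CAD patients match a PAD participant, unmasked investigators choose among them at their discretion, which leaves an avoidable opportunity for selection bias of unknown direction and size

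*Combined protocol and SAP*

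**What the plan says.** Section 11.1.1 describes two routes into the study. For PAD, Vascular Program staff "will introduce all PAD patients to the opportunity". For CAD, among patients who have agreed to chart review, "The study investigators will review the patient charts to find a match to a participant with PAD", and then "The study investigator will notify the cardiac rehabilitation staff members conducting the exercise stress test to inform the patient about the study". Section 2.4 says the same of CAD patients, who "will have their patient file reviewed to determine if the patient is an appropriate match to a PAD patient".

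The matching factors are listed three times, and the lists differ:
- Section 5.1: sex, age within 5 years, diabetes, smoking status and rehabilitation supervisor.
- Section 2.4: sex, age, diabetes and supervisor.
- Section 11.1: sex, age within 5 years, diabetes and supervisor.

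Section 5.1 gives matching as the means of controlling confounding. Under Section 4.1, the first assessment, which precedes the chart review, also records current exercise regimen, medications, angina, medical history and a resting ECG. Section 3.2 is directional: "The primary hypothesis is that patients with CAD will have greater improvements in" VO2peak and the 6MWT, with the reverse expected for the WIQ and quality of life. Section 4.3, on avoiding bias, covers patient blinding and the order of limb pressures only. Section 8.1 specifies a time-by-group ANOVA without covariates.

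**The concern.** The study is not randomised, so the PAD–CAD contrast depends on how the comparator is drawn. Matching balances the listed factors and nothing else. If two or more CAD charts satisfy them, the plan gives no order of preference, no random draw and no masking of the person who chooses. That person knows the arm, has a stated expectation for the primary variable, and can see features outside the matching list.

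If the features that sway the choice are related to change over six months, the CAD mean shifts for reasons unrelated to the disease comparison. The unadjusted ANOVA passes that shift straight into the time-by-group interaction. No log of eligible but uninvited CAD patients is planned, so a reader could not see how much choice there was.

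**Working it through.** **1. The plan's own figure.** Section 8.2 states: "Sample size calculations were conducted using an alpha of 5% and a power of 0.8". Its other inputs are a 10 m between-group difference in 6MWT change and a CAD change of 29.6 ± 12 m. Taking 12 m as the common SD and a two-sided test (sidedness is not stated):

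n = 2 × (1.96 + 0.84)² × 12² / 10² ≈ 22.6, so 23 per group.

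This reproduces the stated 23; a one-sided test would give 18. Then 23 × 1.2 = 27.6, which gives the stated 28. This point disputes none of these figures.

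**2. Scales.** Section 8.2 says 28 per group can detect 1.6 ml/kg/min in VO2peak. The implied SD is 1.6 / (2.80 × √(2/28)) ≈ 2.14. With 20% dropout, 28 × 0.8 = 22.4, so about 22 per group are analysed.

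**3. Model of discretionary choice.** The documents give neither the number of matching charts nor their relation to outcome, so both are assumptions:
- k = number of CAD charts that match a given PAD participant.
- r = correlation between the feature that sways the choice and the change in outcome.
- The most favourable of the k charts is always taken, and there is no true PAD–CAD difference.

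Bias in SD units = r × E[max of k standard normals], where E[max] is 0, 0.564, 0.846 and 1.163 for k = 1, 2, 3 and 5. In a two-by-two design the time-by-group interaction is equivalent to a t-test on change. The two-sided rejection rate therefore comes from the noncentral t with df = 42 and noncentrality = bias / √(2/22).

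| k | r | Bias (SD) | 6MWT bias (m) | VO2peak bias (ml/kg/min) | False-positive rate | Share favouring CAD |
|---|---|---|---|---|---|---|
| 1 | any | 0 | 0 | 0 | 5% | half |
| 2 | 0.2 | 0.11 | 1.4 | 0.24 | 6.5% | about 85% |
| 2 | 0.3 | 0.17 | 2.0 | 0.36 | 8.5% | about 93% |
| 3 | 0.3 | 0.25 | 3.0 | 0.54 | 13% | about 98% |
| 5 | 0.3 | 0.35 | 4.2 | 0.75 | 20% | over 99% |

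For example, with k = 3 and r = 0.3: 0.3 × 0.846 = 0.254 SD; 0.254 × 12 = 3.0 m; 0.254 × 2.14 = 0.54 ml/kg/min; noncentrality 0.254 / 0.3015 = 0.84; rate 13%.

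**4. Cross-check.** A simulation with 23 per group and SD 12 m gave two-sided rates of 6.8%, 9.2%, 13.5% and 21.6% for the four selected rows. Outside that range, k = 2 with r = 0.1 gave 5.4%, and k = 5 with r = 0.5 gave 51%.

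**5. Could selection alone produce the design difference?** The difference is 10/12 = 0.833 SD. That needs r = 0.833/1.163 = 0.72 at k = 5 or 0.833/0.846 = 0.98 at k = 3. It is impossible at k = 2, where r would have to exceed 1.

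**The case against.** The case against a stronger reading is substantial, and most of it stands.

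- *Entry to the CAD arm is an open choice from complete charts.* A reader might infer this, but the text does not support it. Candidates must have consented to chart review, match on four or five factors including the supervisor, and agree to join. The approach is made at the exercise stress test, so the described process does not show the selector baseline VO2peak. There may often be only one match, and then nothing to choose.
- *PAD patients are an unselected series.* They are not. All are told of the study, but they first pass surgeon referral, and then the exclusion criteria, their own interest and consent. The asymmetry lies in the investigator matching step alone.
- *The bias must favour CAD.* Nothing in the documents shows that visible features such as current activity predict a larger change. Patients who are already active could have less room to gain, making r zero or negative. For the WIQ and quality of life, the investigators expect PAD to do better. Selection through attendance is partly closed, because the main analysis keeps only patients above 70% attendance in both arms.
- *The bias could never be detected.* Too strong. Section 4.8 collects exercise regimen, medications, smoking status, risk factors and VO2peak, so imbalance on these can be tabulated and adjusted for. Selection on unrecorded impressions cannot.

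What the objection does not remove is the absence of any rule for choosing among several matches, of masking to unmatched information, and of a log.

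**Conclusion.** The point holds as an avoidable weakness in how the comparator is selected. Where more than one CAD patient matches, unmasked investigators with a stated expectation choose freely, with unmatched information in view, and the primary analysis makes no adjustment.

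The documents do not show that bias will occur, which way it would run or how large it would be. The 0.11 to 0.35 SD and 6.5% to 20% rest entirely on the assumed k and r, and on the favourable chart being taken every time; for each k and r they are upper values. On the plan's scales they amount to 1.4 to 4.2 m against 10 m, and 0.24 to 0.75 against 1.6 ml/kg/min. A reader might infer that selection could by itself manufacture the whole hypothesised CAD advantage. The calculation does not support that at these values. The change is worth making because the safeguard is cheap, not because bias has been demonstrated.

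**What to change.** 1. Reconcile the matching lists: smoking status is in Section 5.1 but not in Sections 2.4 or 11.1. State one list and use it throughout; the rule below cannot be applied until this is done.
2. In Sections 2.4, 11.1 and 11.1.1, state that for each PAD participant the eligible, chart-review-consented CAD patients who meet the matching factors are listed by date of initial assessment. The first on the list, or one drawn by a pre-generated random number, is invited. The next is approached only on refusal or ineligibility.
3. Make the choice from a matching sheet that shows only ID, eligibility and the matching factors.
4. Keep a log of patients eligible, invited, refused and enrolled in both arms, and report the counts side by side.

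The cost is an amendment to the recruitment wording and a short form, with no extra patients or procedures. Staff lose some freedom to pick a convenient match, and there may be short delays when a listed patient declines. Where only one patient matches, the rule changes nothing.

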### 11.1.2 A description of who will make initial contact with research participants

Potential research participants will be informed about the study through a cardiac rehabilitation staff member. If interested, the individual will be introduced to one of the study investigators.

### 11.1.3 A description of who will obtain informed consent from research participants.

[name] candidate, will obtain written informed consent from the research participants. [name] has over 4 years of research experience as a research assistant at the University of Toronto's Training and Performance Laboratory under supervision by [name].

## 11.2 A statement of review and approval of the study by the Research Ethics Board before any study related procedures commenced.

Participant recruitment and data collection for this study will only begin when approval is given by the Research Ethics Board.

## 11.3. A statement of review and approval of any amendment to the study by the Research Ethics Board before any changes implemented beside these to eliminate immediate hazard to the study participants.

If any changes to the study protocol are planned, the Research Ethics Board will be contacted and informed through an amendment prior to the change being implemented.

## **12.0 Data Handling and Record Keeping**

### 12.1.A description of the process for data recording to ensure accuracy, completeness, legibility, and timeliness of the data.

## Comparing the efficacy of cardiac rehabilitation for patients with peripheral artery disease to patients with coronary artery disease/Protocol #03

Data will be recorded on a data collection sheet and will be reviewed following each study visit to ensure accuracy, completeness, and legibility. We hope to begin data collection in January 2018 and complete data collection by December 2018.

### 12.2 A description of where the data will be recorded

Data will be recorded on a data collection sheet and will be stored in a locked cabinet in the TRI Rumsey Centre room 231.

